## **2 HYPOTHESIS, OBJECTIVES, AND ENDPOINTS**

We hypothesize that hypofractionated adjuvant radiation therapy for resected head and neck cancers (HART-HN) may be safely delivered in as few as 5 fractions after surgery in intermediate-risk HNSCC patients. To test this, we propose a Phase I radiation hypofractionation trial in patients with resected head and neck cancers who would require adjuvant radiation for intermediate risk factors (detailed below). This allows us to establish the safety of this regimen in patients for whom locoregional therapy is critical. If HART-HN is shown to be safe and demonstrates a signal of efficacy, this Phase I trial will serve as a foundation for future trials comparing HART-HN with conventional six-week adjuvant radiation therapy.

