### **2.2 Secondary Objectives**

1. To evaluate the efficacy of the HART-HN regimen at the minimum number of safe fractions at 1-year as measured by locoregional control and overall survival
2. To assess patient quality of life during and after the HART-HN regimen at the minimum number of safe fractions as measured by a battery of patient quality of life and functional metrics.

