### **2.4 Secondary Endpoint(s)**

1. 1-year locoregional control of patients receiving HART-HN (efficacy objective)
2. 1-year overall survival of patients receiving HART-HN (efficacy objective)
3. Temporal changes in the CTCAE version 5.0 scores (quality of life objective)
4. Temporal changes in composite FACT-HN scores, composite MDADI scores, opioid use, EAT-10 questionnaire scores, Functional Oral Intake (FOIS) scores and Dynamic Imaging Grade of Swallowing Toxicity (DIGEST) grading (quality of life objective)

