## **7 STATISTICAL CONSIDERATIONS**

### **7.1 Study Design**

This is a Phase I dose-hypofractionation trial of radiation dose using a novel radiation treatment regimen called HART-HN. The primary objective of the study is determine the safe reduction of the number of fractions (10, 8, or 5), of the HART-HN regimen, that may be delivered safely in resected HNSCC patients with intermediate pathologic risk features, using the Time-to-Event Continuous Reassessment Methodology design. This will be determined as the radiation dose with the minimum number of fractions at which there is no more than a 33% rate of dose-limiting toxicity (DLT) up to 12 months after completion of radiation treatment (to allow for the development of late toxicities from radiation treatment). There will be three radiation dose levels (all with a BED3 of approximately 100 Gy) evaluated to the operative bed: 42 Gy in 10 fractions (Dose Level 1), 39 Gy in 8 fractions (Dose Level 2) and 32.5 Gy in 5 fractions (Dose Level 3). The total sample size for this study is 18 patients to be recruited over 12 months.

TITE-CRM is an adaptive Phase I trial design methodology which allows for MTD-finding by weighting the follow-up contribution of previously enrolled patients to the selection of the dose level for each newly enrolled patient. If a patient dies of disease progression without evidence of radiation-related toxicity, they will be censored for

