toxicity at the time point of last follow-up. Thus, TITE-CRM allows for dose modification even if patients have not completed the entire follow-up period. At the enrollment of each new patient, beyond the three initial patients who will receive the lowest dose of 42 Gy), all available follow-up for all patients already on study will be used to determine the dose level for the newly enrolled patient based on the TITE-CRM methodology. For example, if three patients are enrolled every two months, by month seven, the first patient (who enrolled in month 1) provides up to 6 months of follow-up whereas the ninth patient (who enrolled in month 6) provides only about 1 month of follow-up. All available follow-up data from the first nine patients will be used by the TITE-CRM model to make a decision on the dose for the tenth patient. Unlike a standard 3+3 design, the TITE-CRM model may maintain the current dose level, increase the dose level or decrease the dose level based on all available follow-up data at the time of enrollment of the tenth patient.

To implement the TITE-CRM model, we will be using the `titecrm` function from the R package `dform`. An unconstrained TITE-CRM model potentially allows for rapid early dose escalation from Dose Level 1 to 3. To prevent this overly aggressive dose escalation we will require at least 3 sequential patients at each dose level, prior to escalating dose. Further, in the case of rapid enrollment of 3 sequential patients at a new dose level, enrollment will be paused until one of these patients experiences a DLT or a minimum of 3 months elapses from the initiation of radiation treatment for these 3 patients.

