## 7.2 Objectives and Analysis Plans

### 7.2.1 Primary Objective and Analysis Plan

The primary objective of the study is to determine the safe reduction of the number of fractions (10, 8, or 5), that may be delivered safely in resected HNSCC patients with intermediate pathologic risk features.

The minimum number of safe fractions will be determined as the radiation dose at which there is no more than a 33% rate of dose-limiting toxicity (DLT) up to 12 months after completion of radiation treatment (to allow for the development of late toxicities from radiation treatment) using the TITE-CRM design.

A DLT will be defined for the purposes of this protocol as an inability to complete radiation treatment within 30 days of the start of radiotherapy not deemed to be related to disease progression or unrelated death, unacceptable toxicity within one year of treatment (Grade 4+ toxicity) probably or definitely related to radiation treatment as deemed by the treating physician, or a death within one year of treatment deemed probably or definitely related to treatment. Expected Grade 3 acute toxicities typical of head and neck radiation that resolve within 90 days of treatment, including acute dermatitis, acute mucositis, feeding tube placement, electrolyte abnormalities, pain requiring narcotic medication and dehydration requiring IV hydration will **NOT** be considered DLTs. Grade 4+ late toxicities that may be considered a DLT of radiation include but are not limited to:

- Chondronecrosis of the laryngeal cartilages
- Laryngeal edema requiring tracheostomy
- Carotid blowout syndrome or other life-threatening vascular bleed
- Aspiration pneumonia requiring ICU admission not related to tumor progression
- Chronic non-healing wound or soft tissue necrosis requiring flap reconstruction
- Brainstem necrosis
- Radiation myelopathy

Death deemed unrelated to radiation (such as death due to malignancy or other comorbidity) will not be considered a DLT.

All patients who initiate radiation therapy will be evaluable for the primary endpoint as long as they initiate radiation therapy.

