### 7.3 Sample Size Justification

The projected sample size will be 18, and we estimate an accrual rate of 3 patients every 2 months for a total estimated accrual time of 12 months. Patients will be recruited for the study based on whether they are unsuitable candidates for full course definitive chemoradiation either due to inability to tolerate cisplatin, locoregionally recurrent disease after surgery, or de novo metastatic disease. Based on our tumor board presentations, we typically have 6 patients who meet these criteria every month, so the proposed study of 18 patients can be easily accomplished within 12 months of opening if we are able to enroll 25% of eligible patients on this trial. We estimate an accrual of 3 study patients every 2 months (1.5 patients per month)

A review of patients treated at our institution with conventional post-operative radiotherapy from 2017-2019 had a one-year Grade 4+ toxicity rate of 9.5% with a one-year overall survival of 75%. As hypofractionated radiation has similar toxicity rates to conventional fractionation and non-inferior disease control in other malignancies, it is reasonable to expect that the HART-HN regimen may have a similar rate of late toxicity (9.5%) and at least similar survival outcomes to our patient population. In order to demonstrate the feasibility of detecting the correct MTD of the HART-HN regimen with a sample size of 18 patients, we performed Monte-Carlo simulation studies (1000 resamples each) with various *a priori* estimates of toxicity at the three doses (Table 1). For these simulations the following assumptions were made: (1) a constant hazard of observing DLT through the 12-month follow-up period; (2) a one-year survival of 75.4% (constant hazards as well); (3) a study accrual rate of three patients every two months; (4) toxicity as a function of dose level is modeled empirically; and (5) enrollment suspension prior to dose escalation as detailed at the end of section 7.1.

**Table. Results of Monte Carlo Simulation Studies Across Different Assumed Dose-Toxicity Profiles** (Bolded Numbers Reflect Values for the MTD Based on the Assumed Toxicity Profile)

Assumed 1-year toxicity rates at 42 Gy in 10 fractions, 38 Gy in 8 fractions and 32.5 Gy in 5 fractions	Probability that MTD is declared at 30, 32.5 or 35 Gy and the probability that the stopping rule is invoked
5%, 15%, 30%	15.9%, 28.2%, 55.9% , 0.0%
10%, 15%, 25%	24.4%, 25.2%, 50.3% , 0.1%

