10%, 30% , 50%	51.0%, 27.8% , 21.1%, 0.1%
30% , 45%, 60%	86.0% , 6.2%, 1.1%, 6.7%

The probability of correctly identifying the MTD depends on the assumed toxicity at each dose level. However, using a wide variety of assumed toxicities at each dose level and a sample size of 18, results in a good probability of detecting the MTD for the majority of *a priori* estimates. Further, the chance of incorrectly selecting a dose level higher than the true MTD is reasonable (~20% or less at each assumed toxicity level).

No confidence intervals will be constructed due to the small sample size of our study.

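### Section 7.3 rules out confidence intervals because the sample is small, and no other measure of precision is planned for the 12-month DLT rate, locoregional recurrence or overall survival

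*Combined protocol and SAP*

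**What the plan says.** The sentence "No confidence intervals will be constructed due to the small sample size of our study" closes section 7.3, directly after the simulation table, and carries no exception.

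The analyses it affects are in section 7.2:
- **DLT (7.2.1).** TITE-CRM picks the level with "no more than a 33% rate of dose-limiting toxicity (DLT) up to 12 months after completion of radiation treatment". No standard error or interval is named.
- **Locoregional recurrence and overall survival (7.2.2).** These are estimated at one year by a Fine and Gray competing-risk cumulative incidence and by Kaplan-Meier. No standard error or interval is named for either.
- **Quality of life (7.2.2).** This is descriptive only. The exclusion of inferential statistics there is confined to quality of life and does not explain the wider sentence in 7.3.

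The only probability statement about a DLT rate is the accrual-suspension rule in section 7.4. It concerns Dose Level 1, uses a 95% threshold, and serves monitoring, not reporting.

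On use of the results, section 2 makes the trial a foundation for comparative studies "If HART-HN is shown to be safe and demonstrates a signal of efficacy". The first aim in section 2.2 reads: "To evaluate the efficacy of the HART-HN regimen at the minimum number of safe fractions at 1-year as measured by locoregional control" and overall survival.

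**The concern.** The stated reason runs the wrong way. A small sample makes an interval wide; it does not make it invalid. Exact and Bayesian intervals can be computed at this size, and an interval describes precision without being a hypothesis test. Small trials are also where a bare point estimate is most easily over-read.

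Readers will set the results beside the figures in section 7.3: the institution's 9.5% one-year Grade 4+ toxicity, its 75% one-year survival, and the 33% DLT limit. Without intervals they cannot see which of those values the data exclude. The omission is also hard to square with section 7.4, whose suspension rule already needs a probability distribution for the DLT rate while the trial runs.

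**Working it through.** **1. The plan's own figures.** Section 7.3: "The projected sample size will be 18, and we estimate an accrual rate of 3 patients every 2 months". Then 18 / 1.5 per month = 12 months, and 25% of 6 eligible patients per month = 1.5 per month; both agree with the text. The table gives correct-selection probabilities of 55.9%, 50.3%, 27.8% and 86.0%. These cannot be reproduced, because the documents give neither the skeleton nor the prior.

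**2. How many patients a level can hold.** Section 7.1 starts three patients at Dose Level 1 and adds: "we will require at least 3 sequential patients at each dose level, prior to escalating dose". With N = 18 the maxima are:
- Level 1: 18
- Level 2: 18 − 3 = 15
- Level 3: 18 − 3 − 3 = 12

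The documents do not give the expected number at the selected level.

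**3. Exact binomial limits for DLT (Clopper-Pearson, two-sided 95%).** For 1/12 the upper limit p solves (1−p)^12 + 12p(1−p)^11 = 0.025. At p = 0.385 the left side is 0.0029 + 0.0220 = 0.0249, so the limit is 38.5%. For zero events the limit is 1 − 0.025^(1/n).

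| DLTs / n | Estimate | 95% interval |
|---|---|---|
| 0/9 | 0% | 0 to 33.6% |
| 0/12 | 0% | 0 to 26.5% |
| 1/12 | 8.3% | 0.2 to 38.5% |
| 3/12 | 25.0% | 5.5 to 57.2% |
| 2/9 | 22.2% | 2.8 to 60.0% |

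On raw counts, then, one DLT in a Level 3 group of the largest possible size does not exclude 33%.

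**4. Overall survival.** At the institutional 75%, 18 patients give 0.75 × 18 = 13.5 survivors. The nearest whole counts are 14/18 = 77.8% (52.4 to 93.6%) and 13/18 = 72.2% (46.5 to 90.3%). With 12 patients, 9/12 = 75% (42.8 to 94.5%). These ignore censoring, so they illustrate scale only.

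**5. Model-based limits for DLT.** TITE-CRM uses the data from all levels, so step 3 is not the interval the design itself would give. With the empiric model, p_j = s_j^exp(β), and β has a normal prior with mean 0 and variance 1.34 (assumed). The posterior is proportional to the prior times the product over levels of p_j^(DLTs) × (1−p_j)^(non-DLTs), with full follow-up assumed. Five skeletons were assumed: 10/20/33, 9.5/20/33, 20/33/46, 33/46/58 and 5/15/33%.

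The 95% credible intervals at Level 3 were:
- 0/3, 0/6 and 2/9 DLTs at Levels 1, 2 and 3: lower limit about 4%, upper limit 38 to 41%.
- 0/3, 0/3 and 3/12: lower limit about 7%, upper limit 43 to 45%.
- 0/3, 0/3 and 1/12: lower limit about 1%, upper limit 28 to 31%.

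The first two span 33%; the third falls just below it. A point estimate alone would not show the difference.

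**The case against.** The strongest reply has four parts.

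1. **The primary result is a choice of level, and its uncertainty is already quantified** by the simulation table and, for Level 1, by the 7.4 rule. This is true, but the table describes how the design behaves before any data exist, and the 7.4 rule governs accrual. Neither attaches precision to an estimate from the completed trial.

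2. **The sentence bars confidence intervals and does not mention credible intervals.** It also sits in the sample-size section. This stands as to wording: a posterior interval is not expressly forbidden. But nothing in 7.2 plans one.

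3. **Usual Kaplan-Meier and cumulative-incidence intervals rest on large-sample theory, and coverage at an adaptively selected level may not be nominal.** This stands. It calls for small-sample methods and a descriptive label, not for omission.

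4. **If counts by level are published, readers can compute binomial intervals.** This is true for DLT if the counts appear. It does not serve censored survival or competing-risk estimates.

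Some stronger readings are tempting, and the documents do not support them. A reader might infer that the DLT estimate rests on some 6 to 12 patients. That number is not in the documents, and the TITE-CRM estimate draws on every treated patient. A reader might take 2/9 to mean that the planned analysis is compatible with a 60% DLT rate; that is the raw binomial limit, and step 5 gives about 40%. A reader might also infer that results at other levels would go unreported. Section 2.4 defines the efficacy endpoints for patients receiving HART-HN, and section 7.4 says all side effects will be reported.

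**Conclusion.** The point holds as a weakness in planned reporting. It does not invalidate the design or the level-selection rule. The exclusion is explicit, its reason is unsound, and 7.2 offers no substitute.

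The firm part of the size rests on the 12-patient cap at Level 3 and the total of 18: an upper DLT limit of 38.5% for 1/12, and survival of 52% to 94% for 14/18. Both are binomial and ignore censoring. The model-based DLT intervals are narrower and depend on an assumed skeleton, prior variance and full follow-up. Under those assumptions the limit at Level 3 still exceeds 33% with 2/9 or 3/12 DLTs there, but not with 1/12. Any figure for the number of patients at the selected level is likewise an assumption.

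No planned decision rule depends on an efficacy interval. What is at stake is how safely others can read the results when planning the comparative trial that section 2 foresees. The difference in analysis population between section 2.4 and sections 2.2 and 7.2.2 is a separate matter.

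**What to change.** Delete the sentence in section 7.3 and add to section 7.2, labelled as descriptive:

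- **DLT:** raw counts by dose level, with 95% posterior credible intervals for the 12-month rate at each level from the final TITE-CRM fit. State the skeleton and prior used.
- **Overall survival and locoregional recurrence:** 95% intervals for the 12-month Kaplan-Meier and cumulative-incidence estimates, by a named method suited to small samples, such as log-log transformed or beta-product type limits. Report these by level and pooled over all treated patients, which serves either reading of the efficacy population.
- **Caveat:** a sentence saying that coverage at an adaptively selected level may not be nominal.

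The cost is a short amendment to the analysis text and a few lines of code, with no added patients, visits or design change. The downside is small: wide intervals that look less favourable, and the coverage caveat.

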#### **7.4 Study Monitoring, Interim Analyses, and Early Stopping Rules**

This is a Phase I clinical trial. Patients will receive continued follow-up during and after treatment up to 12 months after completion of the HART-HN regimen. All side effects will be reported and any adverse events will be reported to the IRB as per national and local clinical trial requirements. The project is monitored at all times by the Principal Investigators and/or co-investigators. A physician is present at all exams. The Institutional IRB reviews each project yearly. If at any time during the study, there is a greater than 95% probability that the 12-month of Dose Level 1 exceeds 33%, accrual will be suspended temporarily. Accrual will only resume, if, after further follow-up, this probability is less than 95%.

**Adverse Event Reporting:** Any adverse event such as unanticipated or severe toxicity from radiation would be reported to the IRB under the guidelines as required by our Institution. Any DLT will be reported to the MCW DSMC within 5 calendar days of the study staff's knowledge of such an event.

#### **Patient Discontinuation from Study**

Patients have the right to voluntarily withdraw from the study at any time for any reason. In addition, the investigator has the right to withdraw a patient from the study at any time. Reasons for patient discontinuation from the study may include, but are not limited to, the following:

- Patient withdrawal of consent
- Study termination
- Adverse event
- Loss to follow-up
- Patient non-compliance, defined as failure to comply with protocol requirements as determined by the investigator or Sponsor

Every effort should be made to obtain a reason for patient discontinuation from the study. The primary reason for discontinuation from the study should be documented on the appropriate eCRF. If a patient requests to be withdrawn from the study, this request must be documented in the source documents and signed by the investigator. Patients who withdraw from the study will not be replaced.

If a patient withdraws from the study, the study staff may use a public information source (e.g., county records) to obtain information about survival status.

## **Study Discontinuation by PI**

The PI has the right to terminate this study at any time. Reasons for terminating the study may include, but are not limited to, the following:

The incidence or severity of adverse events in this or other studies indicates a potential health hazard to patients. Patient enrollment is unsatisfactory.

## **8 DATA AND SAFETY MONITORING PLAN (DSMP)**

### **8.1 Data and Safety Management Overview**

The Medical College of Wisconsin (MCW) Data Safety Monitoring Committee (DSMC) and the MCW Institutional Review Board (IRB) will approve protocol-specific DSM plans. A local, investigator-initiated trial will be required to be continuously monitored by the principal investigator of the study with safety and progress reports submitted to the DSMC.

The DSMP for this study will involve the following entities:

### **8.2 Study Team**

The study team minimally consists of the principal investigator, the clinical research coordinator, regulatory specialist, and the study biostatistician. While subjects are on study, the principal investigator will meet regularly with the research coordinator and the study biostatistician to review study status. This review will include but not be limited to reportable SAEs and UPIRSOs and an update of the ongoing study summary that describes study progress in terms of the study schema. The appropriateness of further subject enrollment and the specific intervention for a next subject enrollment is addressed. All meetings including attendance are documented.

### **8.3 Quality Assurance**

The MCW Radiation Oncology ROCKET program and CCCTO will provide ongoing quality assurance audits. This protocol was classified as high risk and will be reviewed internally by the MCW Cancer Center Clinical Trials Office Quality Assurance Staff according to the MCWCC Data and Safety Monitoring Plan and current version SOP, 6.5.2 Internal Quality Assurance Reviews.

### **8.4 Clinical Trials Office**

The MCW Radiation Oncology ROCKET program will provide administrative assistance and support to the DSMC.

### **8.5 DSMC**

The Medical College of Wisconsin Cancer Center places the highest priority on ensuring the safety of patients participating in clinical trials. Every cancer interventional trial conducted at MCW includes a plan for safety and data monitoring.

More information can be found related to the MCWCC Data and Safety Monitoring Plan at the MCWCC website ([Data and Safety Monitoring Plan](#)).

This study will be reviewed by the Medical College of Wisconsin Cancer Center Data and Safety Monitoring Committee (MCWCC DSMC). A summary of the MCWCC DSMC activities are as follows:

- Review the clinical trial for data integrity and safety
- Review all DSM reports
- Submit a summary of any recommendations related to study conduct
- Terminate the study if deemed unsafe for patients

A copy of the MCWCC Data and Safety Monitoring Plan and membership roster will be maintained in the study research file and updated as membership changes. The committee will review reports from the study PI twice annually (or more frequently if needed) and provide recommendations on trial continuation, suspension, or termination as necessary.

Any available DSMC letters will be submitted to the IRB of record as required.

